## **PURPOSE OF THE STUDY AND BACKGROUND**

### **2. Purpose of the Study**

#### **What are the specific scientific objectives of the research?**

The primary objective of this research is to determine the impact of oxytocin on irritability and emotional dysregulation in children and adolescents with DSM-V disruptive mood and behavior disorders. It will also examine the impact of oxytocin on the neural response in the amygdala as well as fronto-amygdala connectivity dysfunction related to irritability and emotional dysregulation in children and adolescents, using fMRI and MEG. Changes in symptom profiles as a result of oxytocin treatment will be assessed for correlation with neural level changes. Differences in the magnitude of treatment responses to oxytocin as a function of polymorphisms in the oxytocin receptor (OTR) will also be assessed.

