## **CHARACTERISTICS OF THE SUBJECT POPULATION**

### **4. Accrual**

**Is this study conducted solely at sites under the oversight of the Joint Pediatric IRB (e.g. UNMC, TNMC, CH&MC, UNO)?**

Yes

**A. What is the total number of subjects (per group, as applicable) needed to complete the research in order to achieve the scientific objectives of the research?**

104 subjects are needed to complete the trial (52 per treatment group).

**B. What is the statistical or other justification for the total number of subjects needed to complete the research in order to achieve the scientific objectives of the research?**

The primary outcome is the change of Affective Reactivity Index (ARI) from the baseline to the last visit. A sample size of n=52 per group will provide 80% power to detect a difference between the group means of -4.0 in the change of ARI of -4.0 at the significance level of

0.05 using a two-sided two-sample t-test, assuming the mean of -4.0 and the standard deviation of 7.2 in the oxytocin group, and the mean of 0 and the standard deviation of 7.2 in the placebo group.

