##### **B. What is the age range for the child subjects, and what is the justification for selecting this age range?**

The age range for the child and adolescent subjects in this study is 10-18 years. The disorders included in this protocol have an onset of symptoms in childhood and adolescence

(American Psychiatric Association, 2013). The proposed age range in this protocol was also guided by our previous experience at National Institute of Mental Health conducting neuroimaging studies in youth with disruptive behavior disorders. In our experience, by age 10, 80-90% of participants can be successfully scanned and data are not often compromised by movement.

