**Symptom Profile Assessment:**

The Affective Reactivity Index (ARI) will be completed at the initial research assessment session and the final research assessment session. ARI is a 7 item inventory (self-report

and parent-report versions) specifically designed to measure irritability and emotional dysregulation (Stringaris et al., 2012). This will be used to measure the outcome of improvement in irritability by oxytocin treatment.

The Behavior Assessment System for Children, second version (BASC-3) will be completed at the initial research assessment session and the final research assessment session. BASC-3 is parent-reported, well-established scale for externalizing/internalizing problem of children and adolescents (Reynolds, 2015). This will be used to measure the outcome of improvement in emotional dysregulation and other related symptoms (externalizing behavior) by oxytocin treatment.

The Inventory of Callous Unemotional trait (ICU) will be completed at the initial research assessment session and the final research assessment session. ICU is a 24 item inventory specifically designed to measure callous-unemotional trait in children and adolescents (Berg et al., 2013; Frick, 2004). This will be used to measure outcome of improvement in callous-unemotional trait by oxytocin treatment. This will be also used to assess covariate function of callous-unemotional trait on treatment response.

The Reactive-Proactive Aggression Questionnaire (RPAQ) will be completed at the initial research assessment session and the final research assessment session. RPAQ is a 23 item inventory (self-report) specifically designed to measure two different types of aggressive behavior, i.e., reactive and proactive aggression (Raine et al., 2006). This will be used to measure outcome of improvement in related symptom of aggressive behavior by oxytocin treatment.

The Clinical Global Impression: Severity and Clinical Global Impression: Improvement scales (CGI-S and CGI-I) will be used at study entry and study completion to quantify, based on clinician's global assessment of the individual, the severity of symptoms compared (study entry and completion) and the degree of improvement (study completion) which may or not be attributable to the study intervention. Other symptom profile measurements will be used to assist the clinician in the rating of this measure.

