**Withdrawal Criteria**

1. Initiation of any medication that may have psychotropic effects (newly introduced antidepressants, antipsychotics, anxiolytics, stimulants, and non-stimulant ADHD medications).

2. Discovery of neurologic disorder (including seizures) or anatomical abnormality of brain (including brain neoplasm, hydrocephalus) during participation.
3. Discovery of substance abuse or dependence.
4. Inability of the participant to complete fMRI or MEG due to claustrophobia despite previous questioning.
5. Participants who do not want to continue with the study.
6. Participants who cannot or will not cooperate with study procedures.
7. Participants who experience strong discomfort or develop side effect following the administration of oxytocin or placebo nasal spray.
8. Participants who experience significant worsening of psychiatric symptoms that warrant change of treatment (such as inpatient psychiatric hospitalization).

**G. Describe the specific criteria for halting or early termination of the study (for example statistical evidence of unacceptable toxicity or early demonstration of efficacy or lack of efficacy).**

The study would be halted in followings;

1. Early evidence showing lack of efficacy on irritability or worsening of irritability by oxytocin treatment: After the preliminary phase of the study (10 patients on each arms of oxytocin and placebo trial), if it turns out that children and adolescents experience significant worsening of their psychiatric/behavioral symptoms, or have no change in their psychiatric/behavioral symptoms, we then will consider terminating the study.
2. MEG and/or fMRI become inoperable
3. Serious injury related to procedure (MEG, fMRI, or oxytocin administration) occurs

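### A scanner breakdown, or claustrophobia at the second scan, can cost the final ARI of a child already treated, although the primary analysis needs only a questionnaire

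*Combined protocol and SAP*

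**What the plan says.** Two rules in Section 18 of the combined protocol and SAP make study participation depend on the scanners.

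- Section 18.G lists events on which the study would be halted. Item 2 reads "MEG and/or fMRI become inoperable". It gives no duration, no restart condition and no arrangement for children already on treatment. Item 1 of the same list, on lack of efficacy or worsening, only has the investigators consider termination; item 2 contains no such discretion.
- Section 18.F lists grounds for withdrawing a child from the research. Item 4 is "Inability of the participant to complete fMRI or MEG due to claustrophobia despite previous questioning".

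The primary question is framed without imaging. Section 2 states: "The primary objective of this research is to determine the impact of oxytocin on irritability and emotional dysregulation in children and adolescents". The neural aim follows as an addition: "It will also examine the impact of oxytocin on the neural response in the amygdala". Section 4.B states: "The primary outcome is the change of Affective Reactivity Index (ARI) from the baseline to the last visit". Section 12.B (Symptom Profile Assessment) describes the ARI as a seven-item inventory in self-report and parent-report versions, and schedules it: "The Affective Reactivity Index (ARI) will be completed at the initial research assessment session and the final research assessment session".

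Section 12.B (Oxytocin/placebo administration) starts treatment after the first MRI and MEG visits. It lets the scheduling and completion of the second visits set the length of treatment within 14 to 21 days, and places the final assessment at that time.

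**The concern.** The outcome that sizes the trial can be collected with no scanner running. Under the two rules as written, though, a child who has been randomised and dosed may never reach the session at which the final ARI is taken, for a reason unrelated to measuring irritability.

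The statistical sections (12.F) do not close the gap. They define no intention-to-treat set, no method for missing data and no ARI collection after withdrawal or a halt.

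At stake is avoidable loss of primary data from children in research classified in Section 17 as greater than minimal risk. The loss may also be selective: children who become unable to tolerate a second scan need not be a random subset of those treated. Recruiting replacements restores the numbers but not the missing outcomes.

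**Working it through.** **1. Does the sample size use imaging?** Inputs from Section 4.B: difference in mean ARI change 4.0, SD 7.2 in each group, two-sided alpha 0.05, power 80%, two-sample t-test.

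- Normal approximation: n = 2 × (1.960 + 0.842)² × (7.2/4.0)² = 2 × 7.85 × 3.24 = 50.9, so 51 per group.
- Exact noncentral t, with 2n − 2 degrees of freedom and noncentrality 4.0/(7.2 × √(2/n)): power is 0.793 at n = 51 and 0.801 at n = 52. The smallest adequate n is 52.

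The plan's 52 per group (104 completers) is reproduced from ARI inputs alone. It contains no imaging quantity.

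**2. What each rule acts on, and what the primary outcome needs.**

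| Rule | Trigger | Effect as written | Needed for final ARI? |
|---|---|---|---|
| 18.G item 2 | MEG or fMRI, either one, inoperable | Study halted | No |
| 18.F item 4 | Child cannot complete fMRI or MEG because of claustrophobia | Withdrawn from the research | No |

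The joint conjunction in 18.G item 2 makes the loss of one modality sufficient. Section 3 gives MEG the fronto-amygdala connectivity aim, so a MEG fault alone would trigger the halt.

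**3. A child in mid-treatment.** The baseline ARI exists. The next scheduled ARI is at the final assessment, which sits with the second scans. The interim contact covers symptom level, tolerance and adverse effects, but the ARI is listed only for the initial and final sessions. If the study is halted, or the child is withdrawn at the second scan, nothing in the plan says the final ARI is still taken.

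**4. How large could it be?**

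- For 18.G item 2, the documents give no failure rate for either scanner. As an illustration only, suppose a halt is never lifted and the ARI is analysed on those completed. Under the plan's own assumptions, power would be 0.22 at 10 per group, 0.50 at 26 and 0.68 at 39. These halt points are assumed. They describe a permanent stop, not what continued follow-up of dosed children would recover.
- For 18.F item 4, the documents give no rate of claustrophobia at the second scan. Two features point to a small number: claustrophobia is exclusion criterion 9 (Section 10), and a dosed child has already been through the first MRI and MEG visits.

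**The case against.** The strongest defence is that imaging is no side issue here. The title names the possible mediating role of the amygdala. Section 12.F indexes the purpose by BOLD response as well as symptoms, and Hypothesis A joins the two. Stopping a paediatric trial when its mechanism can no longer be measured is a defensible choice. That stands as far as new enrolment is concerned. It does not explain why an obtainable ARI should be given up in a child already dosed.

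Section 18.G also covers both halting and early termination, so a halt may be a pause, and the 14-to-21-day window could absorb a short outage. The plan's silence on ARI collection after a halt or withdrawal is not a rule to discard data. Both points are fair. They mean the loss is possible rather than certain, and that the text needs to say which applies.

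Several stronger readings are tempting, and the documents do not support them.

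- *Any unfinished scan means withdrawal.* Item 4 is limited to claustrophobia. Item 6, on children who cannot or will not cooperate with procedures, might reach other scan failures, but only on a broad reading.
- *Between 10% and 20% of treated children would be lost.* Section 6.B reports that "80-90% of participants can be successfully scanned", but this is general scanning experience offered to justify the lower age limit. It is not a claustrophobia, withdrawal or second-visit rate, so no power loss should be derived from it. Section 4.C also allows 140 − 104 = 36 consents beyond the completers needed, for screen failures and withdrawals together.
- *Imaging is formally secondary.* The documents never apply that label.

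**Conclusion.** The point holds in a limited form and deserves a change. The halting and withdrawal rules can forfeit the final ARI of children already randomised and treated, while the primary objective, outcome and sample size require no scan. The main issue is 18.G item 2; 18.F item 4 supports it and probably affects few children.

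The size cannot be stated as a rate or a power loss from the documents. The required sample size is unaffected and stays at 52 per group. A reader might infer that these rules will by themselves prevent the primary question from being answered. That would require a permanent halt, which the text permits but does not state.

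The conclusion assumes that the rules are applied literally and that no other document, such as the DSMB charter, secures ARI follow-up. Whether randomisation precedes the first scans is not stated, so the point is confined to children who have received a first dose.

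**What to change.** - **18.G item 2:** state that an inoperable scanner suspends the affected imaging. Whether new enrolment is also suspended is for the sponsor to decide, given the mechanistic aims. Children already dosed still complete the scheduled final ARI assessment and stay in the primary analysis.
- **18.F item 4:** state that inability to complete a scan after the first dose ends the imaging component only, with the final ARI still collected and analysed.
- **Section 12.B (Oxytocin/placebo administration):** end of dosing and the final assessment are anchored to completion of the second scans. If those scans do not take place, the anchor is missing. The sponsor must reconcile these passages with the changed rules; this review proposes no treatment rule.
- **Section 12.F:** define the ARI analysis set and the imaging analysis set separately.

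The cost is an amendment that goes somewhat beyond two sentences, because of the timing passages, and an imaging set smaller than the ARI set that must be reported as such. The sample size does not change.

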**H. Describe plans and resources available to promptly address any subject injury.**

Investigators will be closely monitoring the outcomes of the study and the tolerability of the procedures throughout the conduct of the trial. Additionally, the investigators have expertise in conducting clinical trial in the pediatric behavioral health population, and in the use of fMRI, and MEG.

**19. Potential Benefits to the Subject**

**Are there potential benefits to the subjects that may reasonably be expected from participation in the research?**

Yes

**Describe.**

The diagnostic assessment (K-SAIDS) and symptoms assessment by multiple measurements may provide more comprehensive information about the mental health status of the subject, since they are more thorough and comprehensive than routine clinical

assessment. For example, they may find undiagnosed mood or anxiety issues (major depressive disorder, or social anxiety disorder) that could be informed to the subjects and their parents/guardians for further appropriate treatment and intervention. The subject may experience temporary improvement in irritability and emotional dysregulation with oxytocin treatment for the period of clinical trial.

## **20. Potential Benefits to Society**

**What are the anticipated benefits (i.e., value) to society that may reasonably be expected to result from this research?**

By completion of the study, we aim to obtain better knowledge of treatment and change of pathophysiology in children and adolescents with irritability and emotional dysregulation. This will provide opportunity of improved care for this population by clinicians. It will also hold significant promise in areas such as early and accurate detection of illness, treatment monitoring, and basic understanding of irritability and emotional dysregulation in pediatric population.

## **21. Alternatives to Participation**

**A. How do the study procedures or courses of treatment differ from the care that the subject might receive were he/she not to participate in the research?**

Participants in this study will receive experimental treatment of oxytocin for their irritability and emotional dysregulation. Oxytocin is not approved for the treatment of irritability and emotional dysregulation in pediatric patients and is not commercially available for this. . Diagnostic and treatment of irritability and emotional dysregulation is available in the UNMC department of psychiatry, psychology and other providers throughout the community.

**B. Are there any reasonably available alternatives in the non-research context which would have the potential for providing the same benefits (treatment or other) to subjects?**

Not applicable. There are no direct benefits to subjects; the alternative is to not participate in the research.

◆ Yes. Describe: Regular psychiatric assessment and follow-up with behavioral and/or psychopharmacological intervention can be potentially beneficial for the children and adolescents with irritability and emotional dysregulation. Functional MRI and MEG scanning are not currently used in treatment of disruptive behavior and mood disorders.

No. Explain:

**C. Would any of the study procedures or courses of treatment in the protocol be available to the prospective subject if they elected not to participate?**

No

**Explain.**

Oxytocin is an experimental drug for irritability in pediatric population, and is not part of routine psychiatric treatment.

Functional MRI, MEG, and oxytocin receptor genetic testing are not part of routine psychiatric care for this population. fMRI and MEG are available clinically if indicated and ordered by a medical provider. Oxytocin receptor genetic testing is not likely indicated for any reason at this point beyond the purpose of its use in this study, and would not likely be part of care outside the study.

**D. How do the risks of the research compare with the risks of alternative procedures or courses of treatment described above?**

Participating in the research may involve risk of procedures (oxytocin administration, MRI, and MEG), and loss of confidentiality. The risk of participating in the study is greater than the alternative procedures of treatment.

**E. How do the anticipated benefits of the research compare with the benefit of alternative procedures or courses of treatment described above?**

Oxytocin may not have more benefit than currently available pharmacotherapies or behavioral interventions.

**FINANCIAL OBLIGATIONS AND COMPENSATION**

**22. Financial Obligations of the Parent(s)/Guardian(s) of the Subject**

**A. Who will pay for procedures and treatments performed solely for research purposes?**

Sponsor

◆ Grant

CRC, CCTR

Costs or fees waived by TNMC, UNMC- P, CH&MC or CSP

Subject's health insurance

Medicare/Medicaid

Department/Section funds

Other. Explain.

Parent(s)/guardian(s).

**B. Are there any other financial obligations that the parent(s)/guardians of the subject will incur as a result of participating in the study (e.g. travel expenses, meals, supplies)?**

No

**23. Compensation to the Subject for Participation**

**Will the subject and/or their parent(s)/guardian(s) receive any compensation for participation?**

Yes

**Describe the form of compensation, dollar amount (if applicable) and the prorated compensation plan (if applicable).**

\$20.00 per visit for child

\$20.00 per visit for parent

Since the protocol will have total of 3-5 visits in total, depending on the scheduling of assessment and scan sessions, the total possible compensation for both the child and parent would be \$200.00 ( $\$20.00 \times 5 + \$20.00 \times 5$ ).

A stipend check will be issued at the time of completion of the subject's participation in the study. The check will be issued to the parent/guardian unless otherwise specified.

**PRIOR REVIEW**

**24. Prior IRB Review**

**A. Has this study (or one substantially similar) been previously submitted to the Joint Pediatric IRB (or the UNMC IRB) and then withdrawn by the investigator for any reason?**

No

**B. To the best of your knowledge, has this study (or one substantially similar) been considered by another IRB and not granted approval?**

No

**SUBJECT IDENTIFICATION & RECRUITMENT**

**25. Method of Subject Identification and Recruitment**

**A. Will prospective subjects be identified through initial contact by the investigator?**

Yes

**1) Identified through (check all that apply):**

◆ Clinic

Hospital inpatient units

Previous research participants

- ◆ Investigator, clinic or hospital-maintained databases or registries
- ◆ Other. Explain. Electronic health record

**2) Describe how the research staff has ethical access to the potential subjects.**

Participants will be recruited from the outpatient clinic of the department of psychiatry at UNMC. [name] is faculty in the department of psychiatry. [name] sees patients clinical at the Munroe Meyer Institute, Developmental and Behavioral Pediatrics. Participants will also be recruited from local providers and other community clinics by letter, fliers, and newspaper ads.

Patient's at the outpatient clinic of the department of psychiatry, UNMC will be identified via Epic chart review by the P.I., and designated members of the study team who are also employees of the department of psychiatry and have appropriate access to patient records. The department chair provided permission for the P.I. and study team to access all clinical patient records at the outpatient clinic of UNMC, the department of psychiatry. The P.I. and designated study team members will identify patients potentially eligible for study participation, by reviewing clinical encounters in the Epic chart. The P.I. will then discuss with the treating physicians that their patients may qualify and ask the treating physicians to ask the patient if it would be fine to be contacted for participation in the study. Designated study team members will then coordinate scheduling of study related visits including screening visits and post-enrollment visits and procedures.

**B. Will prospective subjects make the initial contact with the research personnel to inquire about the study?**

Yes

**1) Identified through (check all that apply):**

- ◆ Referral by clinician or other parties specifically for the research
- ◆ Flier
- Newspaper advertisement
- Television spot
- Radio announcement
- ◆ Word of mouth
- Public UNMC study database
- ◆ Other. Explain. Electronic health record; social media (facebook, twitter) using approved flier

